4.4 Exclusion Criteria

- 1. Symptoms such as abdominal, back or limb pain are explained by another condition, as judged by the investigator
- 2. Known or suspected allergy to Panhematin[™] or related products
- 3. A known or suspected allergy to human albumin
- 4. Any disease or condition that the investigator judges would lead to an unacceptable risk to the patient or interfere with the successful collection of data for the trial
- 5. Previous randomization in this trial

All inclusion and exclusion criteria must be satisfied for inclusion of a patient in the efficacy analysis.

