5.5 Blinding

Blinding of treatment with a darkly colored, intravenous drug poses significant challenges, but is feasible because the drug is administered only once, and personnel directly involved in drug reconstitution and administration will be different from those who establish intravenous access and are otherwise involved in the study patient's care. The PI, other physicians, study coordinators and nurses involved in patient care will remain blinded. As described above (Section 5.2), pharmacy personnel (1-2 individuals) and one study nurse who will administer the drug will not be blinded. Blinded staff will not be in the room during study drug administration. Every effort will be made to avoid compromise in blinding if, for example, there are problems with the infusion after it is started. Problems with the infusion will be handled by the unblinded nurse without compromising blinding of other personnel, if possible. Any difficulties that might compromise blinding will be recorded.

Porphyria Laboratory and Center Date: June 18, 2019 IND 13,929

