5.7 Randomization

Treatment in this double-blind, symmetrically randomized, parallel group trial study will be assigned by the study statistician, who will inform the Pharmacy of the assignment. Randomization will be in blocks of 4, and occur after the inclusion and exclusion criteria are satisfied. Labels showing the study randomization number will be generated to label all study samples and materials.

The randomization code for a particular subject can be broken if knowing the identity of the treatment allocation is felt to be necessary for optimal management of the patient and the treating physician concludes that breaking the code is in the best interest of the patient. Whenever a code is broken, the person breaking the code must record the time, date and reasons. It must also be recorded who is unblinded as a result of breaking the code, i.e. specific study personnel and/or the patient.

6. Methods and Assessments

This study will be carried out in an outpatient setting, with an option for inpatient visits if needed, and will consist of screening and enrollment visits (designated Visit 1), followed by a treatment visit for blinded hemin or placebo administration (Visit 2), and post-treatment visits: weekly for the first month, then at3 and at 6 months. Visits 1 and 2 may be combined to occur on the same day.

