8.3 CRF Review and Data Entry

The original CRFs are reviewed by the investigator and study coordinator during the study and after completion of each subject. CRFs are finalized after no further corrections or amendments to the content are expected. After CRFs are verified and finalized, data will be compiled for analysis by the study biostatistician. CRFs will be archived at a secure archiving location at UTMB.

9. Monitoring Procedures

Safety Monitoring Plan

The risk level for this study is judged to be low, since treatment with Panhematin[™] is already part of clinical practice and treatment of enrolled patients, and no investigational products are involved. Although use of albumin for reconstituting Panhematin[™] is an off-label method, there is strong evidence and considerable experience to suggest that this increases safety. Potential risks of the study are described in detail under Assessment of Risks (See Section **13.1** below). Because this is not a Phase III clinical trial, a Data and Safety Monitoring Board (DSMB) is not required.

Recruitment, enrollment, retention, adverse events, and study procedures will be monitored carefully by the PI and study coordinator(s). They will review individual subjects' study records to ensure that appropriate safety procedures are being followed, that protocol requirements are being adhered to, and that data is accurate, complete, and secure. Study records include consent forms, case report forms, flow charts, data forms, laboratory specimen records, inclusion and exclusion criteria forms, adverse event logs, and medical charts. Investigators will review available data at study meetings that usually occur monthly, and discuss any instances of adverse events or unexpected problems encountered regarding patient safety or data collection.

Plan for Adverse Event (AE) Reporting. See Section **7**. The investigators will be notified immediately if an AE occurs, and a medical member of the team will evaluate the patient and enter a note in the CRFs. The investigators will be responsible for notifications to the IRB and others, as appropriate. In particular, all unanticipated, serious, fatal and/or life-threatening adverse events will be reported to the IRB, and others as required, within 24 h of occurrence or notification. The investigators, and the IRB are primarily responsible for determining whether modifications to the protocol and consent form are required. If a determination is

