The data analysis for efficacy will include all randomized subjects who were randomized and exposed to the study drug or placebo, fulfilled inclusion and exclusion criteria, and for whom there were no protocol violations or deviations that affect assessments of efficacy. All subjects exposed to active drug or placebo will be included in the safety analysis.

The decision to exclude any subject or observation will be recorded, and the reasons for their exclusion will be documented and signed by those responsible for the exclusion. This documentation will be stored with other trial documentation.

12. Statistical Analyses

Statistical analyses will be conducted in the Office of Biostatistics at UTMB by [name], Assistant Professor in the Division of Epidemiology and Biostatistics of the Department of Preventive Medicine and Community Health at UTMB.

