12.3 Statistical Methods

All tests for significance will be two sided at the 5% significance level and accordingly 95% confidence intervals will be determined.

The main clinical efficacy variable, the occurrence or nonoccurrence of an acute attack each of the 4 weeks following test infusion, will be analyzed by logistic regression with treatment as a factor and drug dose as a covariate. Data for any post randomization exclusions will be listed and the possible impact assessed.

Use of Panhematin[™] and opioids for treatment of porphyria symptoms during the 4 weeks following treatment will be analyzed by exact two sample Wilcoxon tests or by Fisher's exact test.

Supplementary analyses of the role of demographic and clinical features will be performed.

Adverse events will be coded and analyzed descriptively.

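### The only efficacy set drops randomised, infused patients for ineligibility or unlisted deviations; no as-randomised efficacy analysis is specified and no rule says who decides exclusions

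*Combined protocol and SAP*

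**What the plan says.** Section 11 defines one efficacy set: patients who were randomised and exposed, who "fulfilled inclusion and exclusion criteria, and for whom there were no protocol violations or deviations that affect assessments of efficacy". Section 4.4 says the same about eligibility: "All inclusion and exclusion criteria must be satisfied for inclusion of a patient in the efficacy analysis". The safety set, by contrast, keeps everyone exposed.

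On how exclusions are made, section 11 says: "The decision to exclude any subject or observation will be recorded, and the reasons for their exclusion will be documented and signed". The signatories are described only as the people responsible for the exclusion; their role, blinding status and timing are not given. Section 12.3 adds: "Data for any post randomization exclusions will be listed and the possible impact assessed". It does not say how impact is assessed, on which set, or what follows if the answer changes.

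On replacement, section 3.1 counts a patient as completed only if all entry criteria are met (withdrawal for an adverse event also counts), and section 4.1 replaces patients who do not complete. Section 4.6 replaces enrolled patients found not to meet criteria, but reads mainly as replacement before randomisation. None of these says whether data from an infused patient who is replaced stay in the efficacy analysis.

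**The concern.** Randomisation protects a comparison only while patients stay in it. Here a patient can be randomised, infused and followed, then leave the sole efficacy comparison on a judgement for which the plan gives no list.

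The openings are real:

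- Section 6.1.1 allows randomisation at or before the screening visit, which is also when diagnostic samples are taken. Section 6 allows screening and treatment on the same day, so an eligibility result could arrive after infusion.
- The first exclusion criterion in section 4.4 turns on whether symptoms have another explanation in the investigator's judgement. Those are largely the symptoms that define an attack in section 2.1.
- Section 6.1 records every out-of-window variation as a deviation, and section 5.3 sets a dosing window of ±2 days. Nothing says which variations remove a patient.

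Nor does the plan keep people who know the allocation out of these decisions. Under section 5.7 treatment "will be assigned by the study statistician, who will inform the Pharmacy of the assignment", and under section 12.4 the biostatistician unblinds the data at the interim.

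At stake is whether a result near 5% can be trusted. If the restricted and the full results differ, the plan does not say in advance how the full one counts.

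**Working it through.** **Scale of the trial.** Section 12.4 states 80% power for attack probabilities 0.8 and 0.2 with 10 per group, two-sided 5%. Using the pooled normal approximation:

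- z = [0.6 − 1.96·√(2·0.5·0.5/10)] / √[(0.16+0.16)/10] = (0.6 − 0.438)/0.179 = 0.904, so power is 81.7%. The stated figure reproduces.
- If one patient per arm is excluded and not replaced, z = (0.6 − 0.462)/0.189 = 0.73, so power is 76.8%.

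**How far one or two exclusions can move the result.** The plan gives no exclusion rate and no outcome table, so the tables below are assumptions. The test is the likelihood-ratio test for treatment in a logistic regression with treatment only. The dose covariate planned in section 12.3 is left out. G = 2·Σ O·ln(O/E) on 1 degree of freedom. For 7/10 v 3/10 every expected count is 5, so G = 2·[14·ln(1.4) + 6·ln(0.6)] = 3.29 and p=0.070.

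From each table every single exclusion (20) and every pair (20·19/2 = 190) was enumerated, each patient counted equally.

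| Attacks, placebo v hemin | p, all 20 patients | Singles that cross 0.05 | Pairs that cross 0.05 |
|---|---|---|---|
| 7/10 v 3/10 | 0.070 | 6 of 20 | 15 of 190 |
| 8/10 v 3/10 | 0.021 | 0 of 20 (largest p 0.036) | 105 of 190 |
| 8/10 v 2/10 | 0.006 | 0 of 20 | 0 of 190 (largest p 0.017) |

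Where the counts come from:

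- **7/10 v 3/10, singles.** Dropping any of the 3 hemin patients with an attack gives 7/10 v 2/9. Dropping any of the 3 placebo patients without one gives 7/9 v 3/10. Both have p=0.033, and 3 + 3 = 6. The other 14 give p=0.106.
- **7/10 v 3/10, pairs.** 7/8 v 3/10 (3 ways), 7/9 v 2/9 (3·3 = 9) and 7/10 v 1/8 (3 ways) fall below 0.05, total 15.
- **8/10 v 3/10, pairs.** 6/8 v 3/10 (8·7/2 = 28 ways, p=0.053), 7/9 v 3/9 (8·7 = 56, p=0.053) and 8/10 v 3/8 (7·6/2 = 21, p=0.063) rise above 0.05, total 105.

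The uncorrected chi-square test gives the same counts. Its p-values for the three full tables are 0.074, 0.025 and 0.007.

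Fisher's exact test does not give the same counts. Its full-table p-values are 0.179, 0.070 and 0.023. No single exclusion from 7/10 v 3/10 crosses 0.05. From 8/10 v 2/10, 120 of 190 pairs do: 6/8 v 2/10 (28 ways), 7/9 v 2/9 (8·8 = 64) and 8/10 v 2/8 (28), with p between 0.054 and 0.057.

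**The case against.** **The safeguards are real.** Section 5.7 says: "Randomization will be in blocks of 4, and occur after the inclusion and exclusion criteria are satisfied". Late ineligibility should therefore be uncommon. Section 5.5 says: "The PI, other physicians, study coordinators and nurses involved in patient care will remain blinded". Section 8.3 says: "After CRFs are verified and finalized, data will be compiled for analysis by the study biostatistician". Exclusions must be signed and listed, section 9 has the investigator and coordinator review adherence, and section 15 requires deviations to be documented and reviewed. Anyone who is in fact blind cannot select by arm. All of this stands and lowers the chance of bias. But nothing restricts the decision to blinded people, and no safeguard keeps an excluded patient in a planned comparison.

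**The listing may be enough.** A reader could often rebuild the full table from the listed data. That is true, but a reconstruction has no pre-specified standing if it disagrees with the reported result.

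**The numbers depend on the tables and the test.** Any 20-patient result near 5% is fragile, the tables are assumed, dose is omitted, and the design result does not flip on the likelihood-ratio test. This stands. Fisher's test changes the picture in both directions, so it does not remove the concern.

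**The proposed set is not full intention-to-treat.** It still omits patients randomised but never infused, as section 11 already does. That is correct: the point here is confined to infused patients.

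**Missing outcomes.** An infused patient without a first-week outcome cannot enter the model unless a rule is stated. That also stands, and the rule has to be written.

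**Stakes.** Section 1.3 says the study will not be definitive for labelling, and section 9 says it is not Phase III. This limits how serious the point is without answering it.

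**Conclusion.** The concern holds. One efficacy set is defined, and it removes randomised, infused patients for ineligibility or for deviations that are not listed. No efficacy analysis keeps all infused patients in their assigned arms, and no role is named to decide exclusions.

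The size is that of a small trial: one or two exclusions can move a near-threshold result across 5% in either direction without anyone targeting an arm. A result as strong as the design assumption is robust to this on the likelihood-ratio and chi-square tests, though not to every pair on Fisher's test. These figures rest on assumed tables, equal weight for each possible exclusion and a model without dose. They show fragility; they do not estimate how often exclusions would happen or imply that any would be biased. The point should be corrected because the remedy is cheap; it does not invalidate the design.

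**What to change.** - **Sections 11 and 4.4:** define the primary efficacy set as all randomised patients who started a blinded infusion, analysed by assigned arm whatever is later found about eligibility or deviations.
- **Section 11:** keep the present set as a per-protocol sensitivity analysis and list the deviations that remove a patient or an observation from it. Have exclusions decided and signed by arm-blinded study staff before data are compiled for analysis. The study statistician, the unblinded pharmacy staff and the infusion nurse should take no part.
- **Section 12.3:** state that the impact of exclusions is assessed by reporting the two results side by side, with the full set as primary. Add a rule for an infused patient whose outcome is missing.
- **Sections 4.1 and 4.6:** state that an infused patient who is replaced stays in the primary analysis.

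The cost is protocol wording and one further run of the same model, with no added staff or visits. The downside is that a few patients with deviations or late eligibility findings may slightly dilute the estimate. The per-protocol result is still reported alongside.

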12.1 Purposes

The main purpose of the statistical analyses is to test the null hypothesis that observed differences between the two treatment groups could have been produced solely by chance – the alternative being that differences were due to the difference in treatment (i.e. Panhematin[™] vs. placebo) – and to estimate the true differences between measurements for the two treatment groups. The emphasis in the efficacy analysis will be the effects of treatment with Panhematin[™] vs. placebo in preventing a subsequent attack in the week following a single infusion. Attacks occurring at weeks 2, 3 and 4 will also be subject to analysis, since recurrent attacks do not always occur at precisely predictable intervals.

Biochemical parameters, such as urine and serum levels of PBG, will be analyzed also, but will not be primary efficacy measures.

12.2 Variables for statistical analyses

12.2.1 Efficacy variables

The primary efficacy endpoint is the prevention of an acute attack during the first week following a blinded infusion of either Panhematin[™] or placebo, and at other weekly intervals up to one month.

Secondary efficacy and exploratory endpoints include changes in biochemical parameters during treatment, and the effects of genetic, clinical and demographic features on treatment response.

The following biochemical endpoints will be analyzed:

- Urine (or plasma/serum) ALA, PBG
- Urinary total porphyrins, including fractionation of individual porphyrins by HPLC

- Plasma porphyrins, including fractionation of individual porphyrins by HPLC (if elevated initially)
- Fecal porphyrins, including fractionation of individual porphyrins by HPLC (if elevated initially)

Data related to these secondary endpoints will be subjected to descriptive analyses and differences between the treatment groups analyzed for significance as described below.

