- To evaluate in 20 patients who are on a Panhematin[™] prophylactic regimen whether a blinded dose of Panhematin[™] is more effective than placebo in preventing an attack within the next 1-4 weeks.
- To evaluate in these 20 patients whether hemin is as safe and well tolerated as placebo when administered in a blinded fashion. Safety parameters will include the frequency and severity of phlebitis, nausea, vomiting and coagulation abnormalities.

Secondary Objectives:

• To evaluate the biochemical effects of Panhematin[™] in patients treated with Panhematin[™] to prevent attacks of acute porphyria by measuring urinary 5-aminolevulinic acid and porphobilinogen and serum porphobilinogen. This will determine whether biochemical measurements are predictive of efficacy in preventing an attack.

Exploratory Objectives:

- To evaluate effects of clinical features, such as sex, age and the factors that precipitate attacks of porphyria on response to preventive administration of Panhematin[™].
- To evaluate effects of genetic features, including the nature or the *PBGD*, *CPOX* or *PPOX* mutation on response to preventive Panhematin[™]
- To evaluate the use of Panhematin™ reconstituted with 25% human albumin in patients treated to prevent acute attacks of porphyria

Porphyria Laboratory and Center Date: June 18, 2019 IND 13,929

2.1 Endpoints.

The primary efficacy endpoint is whether a Panhematin[™] is more successful than placebo in preventing a porphyria attack within the next 1-4 weeks when given as the patient's usual periodic prophylactic regimen given within approximately one week. Symptoms during past acute attacks should have included severe abdominal pain requiring a narcotic analgesic. An acute porphyric attack is defined by the presence of abdominal pain and one or more other characteristic manifestations such as tachycardia (heart rate 100 per minute or greater), nausea, vomiting, constipation, extremity pain, acute hypertension, low-grade fever, objective evidence of peripheral neuropathy, ileus, dehydration, mild leukocytosis, or hyponatremia. The manifestations of the recurrent attacks should have been similar to each other in nature (although not necessarily in degree or severity). The presence or absence of all such symptoms will be recorded on the CRFs by study personnel who are blinded to the treatment that was given.

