3.1 Type of Trial

The trial is a double-blind, randomized, placebo-controlled, parallel group trial investigating the efficacy and safety of Panhematin[™] for preventing acute attacks in at least 20 patients with well-documented acute porphyria (AIP, HCP or VP). These patients will (1.) have had frequent attacks in the past, with symptoms such as abdominal, back and/or limb pain and diagnosed after exclusion of other causes, and (2.) be on hemin prophylaxis for prevention of frequent attacks. Although clear guidelines have not been developed, it is expected that patients will have had 6 or more attacks in one year before starting hemin prophylaxis. This would be considered justification for a preventive regimen of hemin on clinical grounds. Most patients on hemin prophylaxis are given a single dose once weekly. However, other prophylactic regimens are effective in some patients, such as twice weekly infusions or a series of 3-4 infusions at monthly intervals. Giving only one blinded infusion may not be meaningful for a patient for whom more than a single infusion is needed to prevent attacks. Therefore, patients will

be offered the number of blinded infusions they usually are given within approximately one week for prophylaxis. All infusions for each patient will be either Panhematin[™] or placebo. An interim analysis will be carried out after completion of ~10 patients to assess progress and possibly adjust the sample size. The trial consists of the following:

- A screening visit to determine eligibility and obtain informed consent
- A treatment visit for administration of one or more double blind prophylactic doses of Panhematin[™] or placebo, corresponding to each patient's usual prophylactic regimen. Depending on the regimen, this visit may be completed in one day or after the number of days corresponding to their usual prophylactic regimen over approximately one week.
- Follow up visit at 1, 2, 3, and 4 weeks to assess response to the infusion of Panhematin[™] or placebo. These visits will be in person or by telephone.
- Additional visits may be scheduled if needed, for example for treatment of symptoms.
- Follow-up visits 3 and 6 months after the end of treatment either in person or by telephone

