Patients will have laboratory documentation of one of the acute porphyrias. Molecular documentation is also expected, although rarely a causative mutation cannot be detected. Upon entry into the study they will be given in a blinded fashion one or more preventive dose of either PanhematinTM (4 mg/kg) or placebo. The number of infusions will correspond to the number of prophylactic doses of hemin they customarily receive over approximately one week. A recurrent attack within the next 1, 2, 3 and 4 weeks will represent treatment failures. Because at study entry most patients are expected to be on weekly prophylactic hemin treatment, and hemin is a short-acting drug, emphasis in the analysis will be on attacks occurring within 1 week after study treatment.

Any attacks that occur during the study will be treated according to standard of care, which may include Panhematin[™], either at the study site or at the patient's usual treatment location.

It is intended that 20 patients will complete treatment with a single blinded dose and at least 4 weeks of follow up. A completed patient is one who meets all entrance criteria, has no exclusion criteria and completes the single dosing and at least one week of follow up, or is withdrawn because of an adverse event.

The site for this study is the University of Texas Medical Branch (UTMB) at Galveston. The UTMB Porphyria Laboratory will carry out laboratory determinations related to porphyria as needed for this study. DNA studies to identify the familial mutation are now standard of care and will not be done as part of the study.

Porphyria Laboratory and Center Date: June 18, 2019 IND 13,929

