3.2 Rationale for the trial design

A randomized, double-blind, placebo controlled study design is important for evaluation of clinical efficacy of a treatment or preventive regimen for acute porphyrias because the symptoms of these disorders (e.g. pain) are highly variable and subjective. Physical signs other than pulse and blood pressure are also at least somewhat subjective. A single dose of blinded treatment, or the number of doses corresponding to patients' usual prophylactic treatment over approximately one week, was adopted because a blinded study of an extended course of preventive treatment would require repeated treatment visits to the study site, which is difficult unless a patient lives close to the site. Also, most patients on hemin prophylaxis have been on a preventive regimen for an extended period, and are not available to be studied when prophylactic Panhematin[™] is initiated. On the other hand, many more patients are available who can travel even long distances to UTMB for a study that focusses on prophylactic dosing for less than approximately one week.

A single dose or multiple doses of study drug within approximately one week does not fully test the effectiveness of a continued regimen of hemin prophylaxis. However, if Panhematin[™] prophylaxis is effective in preventing attacks, a difference should be seen between the Panhematin[™] and placebo groups in the effectiveness in preventing an attack over the next 4 weeks. However, some patients may not remain constantly susceptible to attacks, and at times might not have an attack after a single dose of placebo. Therefore, efficacy data will be collected for 4 weeks or until the next time the patient is treated with Panhematin[™] (either for an acute attack or for prophylaxis), whichever is longer. Given the uncertainty of the follow up interval that will be most informative, and other related uncertainties, an interim analysis will be done after the first ~10 patients to see if an adjustment in sample size or other protocol modification may be needed.

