5.3 Timing of administration of Panhematin[™] or placebo

Treatment with Panhematin[™] or placebo should be given within ±2 days of the time a prophylactic dose or series of doses would have been administered. Panhematin[™] is FDA approved at the dosage level used in this study.

It is recommended in product labelling that Panhematin[™] be given once or twice daily. Therefore, in this study a dose of Panhematin[™] will not be given within 12 hours of a previous preventive dose of active study drug. If an attack occurs within 12 hours of the study dose of Panhematin[™] or placebo, open label treatment with Panhematin[™] will be delayed until 12 hours after the last study dose of Panhematin[™] or placebo. If it considered clinically necessary to start open label Panhematin[™] for treatment of the attack in less than 12 hours, the first therapeutic dose for the attack will be blinded, and will be Panhematin[™] if the patient was randomized to placebo, and will be placebo if the patient was randomized to Panhematin[™]. Whether active drug or placebo is given in this instance will be determined by the Pharmacy, where 1-2 individuals will not be blinded.

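### The primary endpoint spans week 1 and weeks 2 to 4 with no single primary test, and the power example and re-estimation name no window

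*Combined protocol and SAP*

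**What the plan says.** - **Section 2 (Objectives) and 2.1.** The primary objective is whether a blinded dose is "more effective than placebo in preventing an attack within the next 1-4 weeks". The primary endpoint in 2.1 uses the same range.
- **Section 3.1.** "A recurrent attack within the next 1, 2, 3 and 4 weeks will represent treatment failures", which reads as four cumulative windows. The section then says that emphasis will be on the first week, because most patients are on weekly treatment and hemin is short-acting.
- **Section 12.1.** The emphasis is on the week after infusion; weeks 2, 3 and 4 are analysed as well.
- **Section 12.2.1.** The primary endpoint is the first week "and at other weekly intervals up to one month". The secondary and exploratory list covers biochemical changes and patient features. Weeks 2 to 4 are not in it.
- **Section 12.3.** The main efficacy variable is attack or no attack in each of the four weeks, analysed by logistic regression with treatment and drug dose. All tests are two-sided at 5%. No hierarchy, alpha split or adjustment is given.
- **Number of infusions.** Under 3.1 patients will "be offered the number of blinded infusions they usually are given within approximately one week for prophylaxis". Section 12.2.1 counts from a blinded infusion without saying which one.
- **Interim.** Section 3.2 gives uncertainty about the most informative follow-up interval as one reason for an interim "to see if an adjustment in sample size or other protocol modification may be needed". Section 12.4 unblinds the biostatistician for it.
- **Power.** Section 12.4 gives 80% power for recurrence of 0.8 against 0.2 with 10 per group, and a total of 40 for 0.8 against 0.38. Neither example states a period, and the re-estimation in 12.4 and 12.5 names none.

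**The concern.** A primary endpoint that holds four time windows, each testable at 5%, lets more than one result be reported as meeting it. On the wording of 12.2.1, a difference seen only in week 3 could be called a primary success without departing from the plan. Nothing bars the window from being settled after the interim, when one member of the team has seen unblinded data.

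The same gap affects the sample size. A recurrence probability has no meaning without a period. If the risks in 12.4 belong to one window and the test uses another, the stated 80% does not describe the trial that will be run.

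**Working it through.** **1. The plan's own figures.** Inputs from 12.3 and 12.4: two-sided 5%, 80% power, two-sample comparison of proportions; 1:1 allocation from 5.7. With pooled variance and p̄ = (p1 + p2)/2,

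n per arm = [1.96√(2p̄(1−p̄)) + 0.8416√(p1(1−p1) + p2(1−p2))]² / (p1−p2)².

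- 0.8 against 0.2: (1.386 + 0.476)²/0.36 = 9.6, so 10 per arm. Exact power of the uncorrected chi-square test at 10 per arm is 80.5%. The stated figure reproduces.
- 0.8 against 0.38: (1.363 + 0.529)²/0.1764 = 20.3, so 21 per arm against the stated 20. The arcsine formula gives 20.0. This is close enough.

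The arithmetic is sound. What is missing is the window.

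**2. False-positive rate if any weekly test can carry the claim.** Null simulation at 10 per arm, independent weeks, 200,000 trials. The weekly risks are assumed.

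| Weekly risk | Week 1 only, chi-square | Any of 4 separate weeks, chi-square | Any of 4 cumulative windows, chi-square | Any of 4 separate weeks, logistic Wald |
|---|---|---|---|---|
| 0.11 | 1.2% | 4.4% | 8.0% | 0.2% |
| 0.20 | 3.0% | 11.5% | 10.4% | 1.7% |
| 0.26 | 3.5% | 13.4% | 10.8% | 4.9% |
| 0.35 | 3.9% | 14.6% | 10.5% | 10.2% |
| 0.50 | 4.2% | 15.9% | 8.0% | 14.7% |

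The Wald column is the planned model with treatment and a dose covariate assumed unrelated to outcome (8,000 trials). Its cumulative rates are 4.1 to 7.9%, and its week 1 rates 0.0 to 3.8%.

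- *Ratio to one week.* For separate weeks the chi-square ratio is 3.8 to 3.9 (for example 11.5/3.0 = 3.8). With within-patient correlation it is 3.7 to 3.9 at 0.2 and 3.1 to 3.4 at 0.5.
- *Fisher's test.* At 10 per arm it gives 0.6 to 5.0% for separate weeks. At 20 per arm, the size 12.4 contemplates after the interim, it reaches about 5 to 10%.
- *Likelihood-ratio test.* In the planned model it exceeds 5% even for one week (6.8 to 9.8%). That is a separate small-sample matter, which naming a window would not cure.

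**3. Sample size when the window differs from the one the risks belong to.** Same formula as step 1. Every conversion between windows is an assumption.

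| 0.8/0.2 are | Test uses | Assumption | Risks compared | Total N |
|---|---|---|---|---|
| the tested window's risks | that window | none | 0.8 / 0.2 | 20 |
| week 1 risks | 4 weeks, cumulative | constant hazard per arm: 1−0.2⁴, 1−0.8⁴ | 0.998 / 0.590 | 30 |
| week 1 risks | 4 weeks, cumulative | later weekly risk 0.05 in both arms | 0.829 / 0.314 | 28 |
| week 1 risks | 4 weeks, cumulative | later weekly risk 0.1 in both arms | 0.854 / 0.417 | 36 |
| week 1 risks | 4 weeks, cumulative | later weekly risk 0.2 in both arms | 0.898 / 0.590 | 62 |
| 4-week risks | week 1 | constant hazard: 1−0.2^(1/4), 1−0.8^(1/4) | 0.331 / 0.054 | 62 |

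The three shared-risk rows use 1−0.2(1−r)³ and 1−0.8(1−r)³, so they assume no treatment effect after week 1. Their exact power at 10 per arm is 65%, 51% and 30%. Under constant hazard with week 1 risks, windows of 1, 2, 3 and 4 weeks need 20, 18, 22 and 30, so intermediate windows cost little or nothing.

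**The case against.** The strongest reply is that the plan already favours week 1. Section 3.1 gives a pharmacological reason, 12.1 repeats the emphasis under the main purpose of the analyses, and 12.2.1 names the first week first. Section 12.3 speaks of one main variable and one logistic regression, which could mean a single model over four weeks with one treatment effect; then there is no inflation. Both points have force. Even so, emphasis is not designation, and 12.3 does not say which model is meant.

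A reader might also infer more than the documents support:

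- **That the trial's error rate is 1−0.95⁴ = 18.5%.** This needs four separate independent tests, each at a true 5%. The chi-square test is not the planned primary test, and Fisher's test is planned only for hemin and opioid use. The Wald rates pass 5% for separate weeks only at weekly risks of 0.35 and 0.50 among those tried.
- **That there are further competing endpoint windows.** Section 3.2 has follow-up for 4 weeks or until the next Panhematin ("either for an acute attack or for prophylaxis), whichever is longer"), but this describes how long data are collected. Section 6.2.1 states when efficacy is expected. Neither defines an endpoint.
- **That weeks 2 to 4 will be missing by design.** A completed patient in 3.1 is one who, among other things, "completes the single dosing and at least one week of follow up", but the sentence before it intends at least 4 weeks. Gaps are possible, not planned.
- **That the re-estimation will be misdirected.** Going to 40 is only to be considered, and estimates of 20 or less and those far above 40 both end at 20.

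The study is also described as not definitive for labelling (1.3) and not Phase III (9), which lowers the stakes.

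**Conclusion.** The concern stands as a gap in specification that should be fixed. Sections 2, 12.2.1 and 12.3 together allow several unadjusted primary claims, and no text makes week 1 the only one.

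If four separate weekly tests were used, the false-positive rate would be about 3 to 4 times that of one week. The absolute level depends on the test: 4 to 16% with uncorrected chi-square at 10 per arm (8 to 11% for cumulative windows) against 1 to 4% for week 1. With Fisher's test it is at most about 5% at 10 per arm and 5 to 10% at 20 per arm. If 12.3 means one model with one treatment effect, there is no inflation from this source.

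The stated 80% power is not wrong. It holds only if 0.8 and 0.2 are the risks for the window tested; otherwise the week 1 and 4-week readings imply 28 to 62 patients under the assumptions shown. The weekly risks, the independence of weeks and the hazard patterns are illustrations, not figures from the documents.

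**What to change.** - In 2.1, 12.2.1 and 12.3, name one primary analysis, tested once at two-sided 5%. The natural choice is any attack within 7 days, since the protocol already stresses week 1. State when the window starts and ends for patients given several infusions.
- A single pre-specified treatment effect over 4 weeks is an acceptable alternative. It would need a rule for follow-up shorter than 4 weeks.
- Make the other windows secondary, either tested in fixed order or descriptive, and say whether they are cumulative or separate weeks.
- State that the interim cannot change the primary window.
- In 12.4 and 12.5, tie 0.8/0.2, 0.8/0.38 and the re-estimation to that window, and restate the power if the assumed risks for it differ.

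The cost is wording only, with three downsides. The other windows can no longer carry a primary claim. The stated power may become less favourable. And 7 days is shorter than the dosing interval of the monthly regimens that 3.1 allows.
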